### ***13.10 Data Review Meeting***

The sponsor will convene a Data Review Meeting after the data has been cleaned and the database locked but before analysis has commenced. The review will be performed within the framework of the requirements of the ICH Guideline E9.

The terms of reference for the Data Review Meeting will include, but will not be limited to:

- the determination of whether protocol violations are 'major' or 'minor', or not a protocol violation at all
- the allocation of subjects to analysis sets
- a review of missing data and of outliers
- a review of the distribution of the efficacy variables, considering any implications for the proposed method of statistical analysis
- a review of whether additional covariates need to be included in the analyses
- revisions to SAP in light of any Data Review Meeting findings

All persons taking part in the Data Review Meeting must only have access to datasets masked to treatment allocation. Treatment group allocations will be scrambled using a dummy randomisation list and presented using generic treatment labels (for example, “Group A” and “Group B”)

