## 4. Timing of planned analyses

### 4.1. Data Review Meeting

The sponsor will convene a Data Review Meeting after the data has been cleaned and the database locked but before analysis has commenced. The review will be performed within the framework of the requirements of the ICH Guideline E9. The datasets used in the review will be masked to treatment allocation and dummy treatment groups with generic treatment labels will be used. The terms of reference for the Data Review Meeting are outlined in Section 13.10 of the protocol.

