- SAEs leading to discontinuation of study treatment

Separate summaries for AEs and SAEs will be created, split by the following:

- Causality (not related, related to the investigational medicinal product (IMP), related to sick day medication, related to an interaction between IMP and sick day medication, related to either IMP or sick day medication)
- Action taken (dose unchanged, dose increased, dose decreased, drug interrupted, drug withdrawn)
- Outcome (Resolved, resolved with sequelae, resolving, not resolved, unknown, fatal)
- By severity (Mild, moderate, severe)

Additionally, all summaries above have the potential to be repeated to show the number of episodes in each category (using total number of patient-years exposed to IMP as the denominator). This is optional and to be done only if there are differences in exposure between treatment groups. A decision as to whether this is required will be made at the Data Review Meeting.

Tables of most common AEs (frequency of >10%) and common SAEs (>1% of subjects overall), will be summarised by preferred term, by decreasing frequency. These thresholds may be adjusted downwards at the Data Review Meeting if there are relatively few subjects with AEs.

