#### Safety

Duration of exposure (Safety analysis set)

Dose titrations recommended by the independent blinded physician (Safety analysis set)

Reasons for dose increases and reductions recommended by the independent blinded physician (Safety analysis set)

Table of dose titrations instructed by the Investigator (Safety analysis set)

Reasons for dose changes instructed by the Investigator (Safety analysis set)

Adverse event in any category - subject level (Safety analysis set)

Adverse event in any category - episode level (Safety analysis set)

Listing of deaths (Safety analysis set)

Adverse events leading to death (Safety analysis set)

Listing of adverse events leading to death (safety analysis set)

All adverse events (Safety analysis set)

All serious adverse events (Safety analysis set)

Listing of all serious adverse events (Safety analysis set)

Adverse events leading to discontinuation of study treatment (Safety analysis set)

Listing of adverse events leading to discontinuation of study treatment (Safety analysis set)

Adverse events by causality (Safety analysis set)

Adverse events by action taken (Safety analysis set)

Adverse events by outcome (Safety analysis set)

Adverse events by severity (Safety analysis set)

*Repeat above 6 tables for SAEs*

Most common (frequency of >10%) adverse events (Safety analysis set)

Most common (frequency of >1%) SAEs (Safety analysis set)

Adverse events leading to use of "sick day rules" (Safety analysis set)

Adverse events leading to use of “sick day rules” by sick day medication (Safety analysis set)

Adverse events leading to Adrenal crises (Safety analysis set)

Adverse events of unexpected therapeutic benefit (Safety analysis set)

*Repeat of AE Tables at episode level to be decided at Data Review meeting*

Signs and symptoms of adrenal insufficiency and over treatment (Safety analysis set)

Haematology (1) laboratory variables (Safety analysis set)

Change from baseline in Haematology (1) laboratory variables (Safety analysis set)

Shift table of baseline to minimum on-treatment for Haematology (1) laboratory variables (Safety analysis set)

Shift table of baseline to maximum on-treatment for Haematology (1) laboratory variables (Safety analysis set)

Haematology (1) results considered clinically significant by the investigator (Safety analysis set)

*Repeat above 5 tables for Haematology (2), Haematology (3)*

Biochemistry (1) laboratory variables (Safety analysis set)

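### Patient-year AE rates hinge on an exposure difference between arms, judged by a meeting that sees only scrambled arms, so the trigger is uninformative

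*SAP*

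**What the plan says.** SAP 11.2 sets out AE summaries as numbers and percentages of subjects. It then allows all the summaries above that point to be repeated as episodes, "using total number of patient-years exposed to IMP as the denominator". Two sentences govern the repeat: "This is optional and to be done only if there are differences in exposure between treatment groups", and "A decision as to whether this is required will be made at the Data Review Meeting". The table list in SAP 14.1 (Safety) carries a matching note: "Repeat of AE Tables at episode level to be decided at Data Review meeting". No size of difference is set and no test is named.

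What the meeting may see is fixed elsewhere. SAP 4.1: "The datasets used in the review will be masked to treatment allocation and dummy treatment groups with generic treatment labels will be used". Protocol 13.10: "Treatment group allocations will be scrambled using a dummy randomisation list and presented using generic treatment labels". Protocol 13.10 applies the masking to everyone who takes part. No unmasked party is given the exposure comparison, and no later step reopens the decision.

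**The concern.** The condition is a fact about the true arms, and the body asked to judge it is barred from seeing them. The protocol says that allocations are scrambled as well as given generic labels. Had the true arms only been renamed A and B, an exposure difference would remain visible and the rule would work. Once allocations are scrambled, the comparison available to the meeting is between two random halves of the trial.

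A difference in exposure is plausible. The trial is open-label. Intolerance of Chronocort heads the list of reasons for stopping treatment (protocol 11.5), and only one arm can meet it. Comparator subjects continue a therapy on which they have been stable for at least 6 months. If one arm is followed for less time, percentages of subjects with an AE tend to flatter it, and rates per patient-year are the usual correction.

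**Working it through.** **Figures from the plan.** It gives none for this rule. Taken from it are 120 randomised (120 × 0.85 = 102 evaluable) and 24 weeks of treatment, 168 days. Assumed, because the documents do not state them: 1:1 allocation (60 per arm), withdrawal rates by arm, and withdrawal times uniform over the period.

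**Expected dummy difference.** If the dummy list is independent of the true allocation, each subject is equally likely to fall in either dummy group. The expected exposure difference is therefore 0 for any true difference.

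**Worked case, 0% versus 20% withdrawal.** Let e be the fraction of 168 days completed.
- A withdrawer loses half the period on average, so the true deficit is 0.20 × 0.5 = 10%.
- Pooled withdrawal is 10%. Mean of e = 0.90 + 0.10 × 0.5 = 0.95. Mean of e² = 0.90 + 0.10/3 = 0.9333. Variance = 0.9333 − 0.9025 = 0.0308, SD 0.176.
- SD of the difference between two dummy groups of 60 = 0.176 × √(2/60) = 0.032, or 3.2 points around a mean of 0.

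**Simulation** (10,000 trials per row, 60 per arm; two possible readings of a difference in exposure, since the SAP sets none):

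| Withdrawal, assumed | True mean difference (days) | Dummy mean difference (days) | t-test p<0.05: true / dummy labels | Gap >5% of 168 days: true / dummy labels |
|---|---|---|---|---|
| 15% / 15% | 0.0 | 0.0 | 4.9% / 4.9% | 19% / 19% |
| 10% / 20% | 8.4 | 0.0 | 26% / 4.7% | 50% / 18% |
| 5% / 25% | 16.7 | 0.2 | 79% / 4.8% | 91% / 19% |
| 5% / 40% | 29.2 | 0.1 | 99% / 4.9% | 99.9% / 28% |

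Under dummy labels the test fires at its false-positive rate throughout. The cruder trigger fires more often only when overall exposure varies more. Neither carries information on the size or direction of the true difference.

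**Effect on subject percentages, worked case.** SAP 11.2 summarises AEs up to the last dose for extension entrants and up to 30 days later for others. Early withdrawers cannot enter the extension (protocol 11.1.9 and 11.5). If all completers enter it, mean AE-counting time in the 20% arm is 0.8 × 168 + 0.2 × (84 + 30) = 157.2 days, a deficit of 1 − 157.2/168 = 6.4%. Assume a constant hazard λ = ln 2/168 per day, so that 50% of completers have an AE. A withdrawer's probability is then 1 − e^(−30λ) × 0.5/ln 2 = 1 − 0.884 × 0.721 = 0.36. The arm shows 0.8 × 0.50 + 0.2 × 0.36 = 47%. The standard error of the difference is √(2 × 0.25/60), about 9 points.

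**Denominator.** Mean on-drug exposure in that arm is 0.9 × 168 = 151.2 days. Dividing events counted over 157.2 days by 151.2 days inflates its rate by 157.2/151.2 = 1.04, about 4%, if the event rate is the same off drug. The other arm is not inflated.

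**Duration formula.** SAP 11.1 subtracts the last-dose date from the first and adds 1. For doses from day 1 to day 168 this gives 1 − 168 + 1 = −166 instead of 168.

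**The case against.** Much of the information arrives anyway. The SAP 11.2 overview gives AE numbers by treatment group, and SAP 14.1 lists an episode-level overview table and a duration-of-exposure table without condition. For any AE, SAEs, sick-day events and Addisonian crises a crude rate is one division away. This stands, and it narrows the loss to the formatted rates and the repeats by system organ class and preferred term.

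A reader might infer that the sick-day and adrenal-crisis tables are themselves suppressed. The SAP text does not support that. The condition covers the summaries above it, and those tables are specified afterwards, in 11.3.1 and 11.3.2, as subject frequencies. Only the general note in SAP 14.1 could reach them.

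A reader might also infer that the rates would almost never be produced: in the worked case a dummy gap of 10 points or more occurs in only about 0.2 to 0.3% of trials. But the SAP sets no such threshold. Even under true labels a gap that large appears in only about 49% of trials, and dummy labels show a gap of at least 5 points in about 11% and at least 2 points in about 53%. The rule fires by chance; it is not that it never fires.

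Pooled masked exposure is also informative up to a point. With equal arms the gap cannot exceed twice the pooled shortfall, so near-complete exposure rules out a large difference. It cannot show whether a difference exists. Further analyses may be added after unmasking (protocol 13.9, SAP 2.4), but the choice would then be made with the results in view.

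**Conclusion.** The point holds as a defect in procedure with limited consequences. A comparison of dummy groups cannot inform a decision about the true arms, and this follows from the text without any numerical assumption. The practical size does rest on assumptions. The only related figure in the plan, 15% inevaluability, is not split by arm and covers protocol deviations as well as withdrawals. Under 0% versus 20% withdrawal exposure differs by 10%, yet the subject percentage moves by about 3 points against a standard error of about 9. With low or balanced withdrawal over a fixed 24 weeks the effect is small. The tables are descriptive and the primary efficacy conclusion is untouched. The documents do not support a claim that the safety comparison would be materially biased. The change is still worth making, because the safeguard fails in the unbalanced case for which it was written.

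**What to change.** 1. In SAP 11.2 delete the condition and the reference to the Data Review Meeting for the episode-level summaries. Delete the matching note in SAP 14.1.
2. Produce episode counts and rates per patient-year by true arm, unconditionally, for the overview categories, all AEs and SAEs. Extend this to the sick-day and adrenal-crisis tables in SAP 11.3.
3. Use as denominator the time over which AEs are counted: to last dose for extension entrants, to last dose plus 30 days for all others.
4. Correct the total-duration formula in SAP 11.1 to last dose minus first dose plus 1.

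Moving the trigger to after unmasking, with a stated threshold, would also work but is weaker: on true labels a p<0.05 trigger flags 10% versus 20% withdrawal in only 26% of trials.

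The cost is a few extra descriptive safety tables. No new data are needed, and nothing has to be unmasked before database lock.

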### 11.3. Adverse events of special interest

#### 11.3.1. Use of “sick days”

As per the protocol each site will have a set of sick day rules where certain AEs will result in emergency hydrocortisone being taken.

All AEs leading to use of “sick day rules” will be summarised (frequency and percentage of subjects) by system organ class, preferred term and treatment group.

In addition, all AEs leading to use of “sick day rules” will also be summarised (frequency and percentage of subjects) by preferred term, route of, and specific sick day medication by treatment group.

There will be a separate listing showing details of all AEs leading to use of sick day rules and specific sick day medication.

#### 11.3.2. Adrenal crises

All AEs leading to adrenal crises as defined in the protocol will be summarised (frequency and percentage of subjects) by SOC, PT and treatment group. There will be a separate listing showing details of all AEs leading to adrenal crises.

#### 11.3.3. Unexpected therapeutic benefit

All AEs leading to unexpected therapeutic benefit will be summarised (frequency and percentage of subjects) by SOC, PT and treatment group. There will be a separate listing showing details of all AEs leading to unexpected therapeutic benefit.

### 11.4. Routine clinical laboratory evaluations

#### 11.4.1. Naming conventions

The laboratory test names will be displayed using test names consistent with the protocol for all reporting. Study Data Tabulation Model (SDTM) standard names will be derived in the dataset, but not displayed. Where needed, an abbreviated version of the laboratory test names may be displayed.

A full list of laboratory display names (full and an acceptable abbreviation) together with their SDTM laboratory test code and name is given in Appendix B for haematology, clinical biochemistry, bone markers and laboratory parameters of special interest, and urinalysis tests.

#### 11.4.2. Haematology

The following haematology parameters will be collected:

Red blood cell count (RBC), red cell distribution width (RDW), haemoglobin (Hb), haematocrit (Hct), mean corpuscular volume (MCV), mean cell haemoglobin (MCH), mean cell haemoglobin concentration (MCHC) platelet count (PLT), white blood cell count (WBC), WBC differential count: neutrophils, eosinophils, basophils, lymphocytes, monocytes (absolute).

All laboratory analyses will be carried out by the central laboratory QSolutions. If laboratory results are needed urgently for safety reasons during the study, these can be processed at the local

laboratory and the results recorded in the electronic case report form (eCRF). For the local lab data, the local reference ranges will be used and if for any reason these are missing, the central ranges will be used, with any such occurrences clearly marked in the listings.

Change from baseline will be calculated at each visit (Week 4, Week 12, and Week 24) and summary statistics will be presented for both absolute values and change from baseline for all haematology parameters by treatment group, pre-baseline standard therapy and visit. Shift tables of baseline to minimum and maximum on-treatment will be produced for the appropriate parameters displaying the number and percentage of subjects in each of the categories (High, Low and Normal) relative to the category of their baseline assessment. Haematology results considered clinically significant by the investigator will be summarised at each visit. Detailed listings will be produced for all haematology parameters. In addition, boxplots of change from baseline in haematology parameters over time will be produced along with a line connecting the mean change through time.

For the purpose of both Listings and Summary Tables, the haematology results will be divided into the following groups of related items:

#### Haematology (1)

- Red blood cell count (RBCs)
- haemoglobin (Hb)
- haematocrit (Hct)

#### Haematology (2)

- red cell distribution width (RDW)
- mean corpuscular volume (MCV)
- mean cell haemoglobin (MCH)
- mean cell haemoglobin concentration (MCHC)
- platelet count (PLTs)

RDW-CV(%) will be provided by the central laboratory. In any local laboratories provide RDW-SD (fL) measurements, RDW-CV(%) will be calculated from the RDW-SD (fl) and MCV measurements using the formula:

- $RDW-CV(\%) = (RDW-SD(fL)/MCV)*100.$

#### Haematology (3)

- total white blood cell count (WBCs)
- lymphocyte count
- monocyte count
- neutrophil count
- basophil count
- eosinophil count

White blood cells (Leukocytes) are made up of Neutrophils + Eosinophils + Basophils +Lymphocyte + Monocyte.

Therefore, to express any of the components as a percentage of Leukocytes, the formula is:

- $Components\ cell\ count/Leukocytes\ counts*100,$  (e.g. Neutrophils count/Leukocytes counts\*100)

However, if the percentage is given and to derive the cell count, the formula is:

- $(\text{Components percentage}/100) \times \text{Leukocytes counts}$ , (e.g.  $(\text{Neutrophils \%}/100) \times \text{Leukocytes counts}$ )
- Note it is important that the component cell count and white blood cell count (Leukocytes) are expressed in the same units when applying these derivations.

### 11.4.3. Clinical biochemistry

The following routine biochemistry parameters will be collected:

Sodium, potassium, chloride, total carbon dioxide (CO2), creatinine, glucose, blood urea nitrogen (BUN), albumin, total calcium, total magnesium, inorganic phosphorus, alkaline phosphatase, alanine aminotransferase (ALT/GPT), aspartate aminotransferase (AST/GOT), total bilirubin, direct bilirubin, lactate dehydrogenase (LDH), total protein, total creatinine kinase (CK), uric acid, total cholesterol, high density lipoprotein (HDL) cholesterol, low density lipoprotein (LDL) cholesterol, triglycerides.

All laboratory analyses will be carried out by the central laboratory QSolutions. If laboratory results are needed urgently for safety reasons during the study, these can be processed at the local laboratory and the results recorded in the electronic case report form (eCRF). For the local lab data, the local reference ranges will be used and if for any reason these are missing, the central ranges will be used, with any such occurrences clearly marked in the listings.

Change from baseline will be calculated at each visit (Week 4, Week 12, and Week 24) and summary statistics will be presented for both absolute values and change from baseline for all clinical biochemistry parameters by treatment group, pre-baseline standard therapy and visit. Shift tables of baseline to minimum and maximum on-treatment will be produced for the appropriate parameters displaying the number and percentage of subjects in each of the categories (High, Low and Normal) relative to the category of their baseline assessment. Biochemistry results considered clinically significant by the investigator will be summarised. Detailed listings will be produced for all routine biochemistry parameters. In addition, boxplots of change from baseline in clinical biochemistry parameters over time will be produced along with a line connecting the mean change through time.

For the purpose of both Listings and Summary Tables, the clinical biochemistry results will be divided into the following groups of related items:

#### Biochemistry (1)

- Sodium
- potassium
- chloride
- total CO2
- total calcium
- total magnesium
- inorganic phosphorus

#### Biochemistry (2)

- creatinine
- blood urea nitrogen (BUN)
- glucose

- uric acid
- total protein
- albumin

#### Biochemistry (3)

- alkaline phosphatase
- ALT/GPT
- AST/GOT
- total creatinine kinase
- lactate dehydrogenase
- total bilirubin
- direct bilirubin

#### Biochemistry (4)

- total cholesterol
- high density lipoprotein (HDL) cholesterol
- low density lipoprotein (LDL) cholesterol
- triglycerides

#### 11.4.4. Urinalysis

The following urinalysis parameters will be collected: protein, specific gravity, ketones, urobilinogen, bilirubin, pH, blood.

For the continuous results (pH and specific gravity), change from baseline will be calculated at each visit (Week 4, Week 12, and Week 24) and summary statistics will be presented for both absolute values and change from baseline by treatment group, pre-baseline standard therapy and visit. In addition, boxplots of change from baseline in continuous urinalysis parameters over time will be produced along with a line connecting the mean change through time.

For all other urinalysis parameters, the frequency and percentage of subjects with results in each category, and shift table of baseline to worst on-treatment will be presented by treatment group, pre-baseline standard therapy and visit. Urinalysis variables will be listed by subject and time point. Values outside the normal ranges (provided with the laboratory report) will be flagged in the subject data listings.

Urinalysis results considered clinically significant by the investigator will be summarised.

A pregnancy test will also be carried out in female subjects of child bearing potential and the results will be listed.

#### 11.5. Vital signs

The following vital signs will be collected: systolic blood pressure (SBP), diastolic blood pressure (DBP), pulse rate, respiratory rate, temperature, height, waist circumference, weight, BMI.

The change from baseline will be calculated and summary statistics will be tabulated for both absolute values and change from baseline by treatment group, pre-baseline standard therapy, and visit. Shift tables of baseline to minimum and maximum on-treatment will be created for the following vital signs: SBP and DBP. In addition, boxplots of change from baseline in vital signs over time will be produced along with a line connecting the mean change through time.

Vital signs will be listed and abnormal findings will be marked.

The following reference ranges will be used to determine the categories for the vital signs shift table, and to mark the abnormal (high/low) findings in the vital signs listing:

- Systolic blood pressure: Low < 100 mmHg; Normal  $\geq$  100 mmHg to  $\leq$  150 mmHg; High > 150 mmHg
- Diastolic blood pressure: Low < 60 mmHg; Normal  $\geq$  60 mmHg to  $\leq$  95 mmHg; High > 95 mmHg

